A 4-arm randomized controlled trial of Fuse, EndoCuff, EndoRings and standard colonoscopy for improving adenoma detection rates.

Protocol:

Introduction:

ADR (Adenoma detection rate or percentage of patients with at least one adenoma among all colonoscopies performed by a doctor) was first proposed as a quality indicator 12 years ago. It has now been validated as an excellent marker for the risk of interval colorectal cancer (cancer occurring after colonoscopy). Although colonoscopy offers protection from colorectal cancer for at least a decade and more, this protection has been shown to vary depending on the location and type of pre-cancerous lesions and the training and skill of the doctor performing the procedure. A recent large study of more than 200,000 colonoscopies found that every 1% increase in ADR resulted in a decrease of interval CRC by 3% and fatal interval CRC by 5%. Although the increase was linear the effect was more pronounced once the ADR reaches 28% and continued beyond till 52%.

Measures to improve ADR are therefore a worthy goal to study. Recent studies indicate that continuing medical education, time of colonoscopy during the day, forced longer withdrawal time, use of high definition colonoscopes all result in improving ADR although the gains have only been modest. To this end, adding novel devices to the tip of colonoscope may improve the ability of doctors to perform a better procedure. We therefore propose to identify the increase in ADR with 3 of these devices compared to standard colonoscopy. Fuse colonoscopy (2 cameras embedded at the side of the colonoscope tip providing an increased angle of view), EndoCuff (a plastic cap to fit the tip with flexible arms which hold the mucosa back aiding in inspection), EndoRings (similar to EndoCuff but the arms are wider) have been shown in tandem colonoscopy studies to improve the adenoma miss rates to 7-15%

instead of the miss rates seen with standard colonoscopy which is usually about 40%. All these devices are FDA approved and are distributed in the United States.

Methods:

Persons scheduled for a standard screening, surveillance or diagnostic colonoscopy at the Glen Lehman Endoscopy Suite will be invited to participate in the study after a member of the research team explains the risks, benefits and the choice of not participating in research.

If the patient qualifies after being screened for exclusion criteria as listed below, they will be given an informed consent document and an authorized HIPAA form to sign. Once both documents are signed, a copy will be provided to the patient and then the patient is randomized to undergo a standard colonoscopy, a Fuse colonoscopy, colonoscopy with EndoCuff or a colonoscopy with EndoRings.

Study procedures:

Patients will undergo a split dose bowel preparation starting the evening before the procedure day and ending at least 4 hrs. prior to the procedure. Patients with medical indicators of inadequate bowel preparation are given a more intensive regimen sometimes doubling the dose of preparation drug. Patients agreeing to participate will be randomized to one of the four study arms prior to initiation of colonoscopy.

A colonoscope will be introduced and advanced to the cecum at which time a research assistant will note the time taken to achieve this. Once the withdrawal starts, the same assistant will start a stopwatch which will be stopped for any cleaning of the bowel or polypectomy procedures. In this way inspection time can be monitored for all arms of the study.

After randomization, a patient can be withdrawn due to condition discovered during colonoscopy which places the patient in the exclusion criteria, an inadequate bowel preparation as determined by the performing doctor or a request from the patient to be withdrawn.

Inclusion criteria:

Screening colonoscopy, Surveillance colonoscopy or diagnostic colonoscopy and ≥ 50 years of age

Exclusion criteria:

Any personal h/o large bowel resection, inflammatory bowel disease, or polyposis syndromes

Any family h/o polyposis syndromes

Referral for an incomplete exam or polyp clearance

Referral for a FOBT+ testing in the last 6 months

Anticipated difficult colonoscopy

Statistical analyses:

We will perform analyses on the data after randomization and prior to withdrawal (intention to treat) and on data of patients completing the study (excluding the withdrawal patients, per protocol).

The primary aim of increased ADR detection will be tested using a chi-square test among the four groups.

The secondary aims of cecal intubation rates, cecal insertion time and detection of serrated and flat lesions will be tested using chi-square, t-test, and chi-square respectively.

All analyses will be performed on SPSS Version 20 (IBM, NY).

Sample size:

The ADR of the principal investigator has averaged about 40% in published studies. We hope to achieve a 10% increase in the ADR with these newer devices when compared to standard colonoscopy.

Using a 4-arm RCT, to detect a 10% increase from a baseline of 40%, we require 388 patients in each arm at an α level of 0.05 with 80% power (n=1552). To account for the withdrawals after randomization, which would amount to an average of 6% per our recent studies, we will need to enroll 412 patients in each arm (n=1648).

Ethical considerations:

All protocols will be approved by the local IRB before starting the research study. An informed consent document will be provided to each patient to review for participating in the study. An express authorization to review medical data for research purposes will be obtained before randomizing any patient. All patients will be provided with a contact number in case of questions or if they wish to inform of their intent to be withdrawn.

Adverse events:

The primary investigator will monitor any adverse event reported to the study staff and determine if it's related to the study procedures including standard colonoscopy. All adverse events will be monitored until a satisfactory resolution and will be reported to the IRB within 5 days of knowledge.

A table will be maintained for the adverse events in each arm and in case of any statistically significant adverse event rate in any arm, the primary investigator will make the decision to remove the treatment arm or stop the study.

Data integrity and safety:

All paper charts pertaining to the patient will be kept under lock and key in coordinators office away from the endoscopy area. The data entry will be performed into an excel file which will be stored on an internal network drive with encryption and password security. Only approved personnel by the IRB will have access to the file storage. This file will also not have any identifiable information (name, DOB or mrn). A study log with the identifiable information will be kept in a separate folder (also encrypted) to enable the investigators to assist in any research audit. No procedural data except the date of examination will be entered into this log.

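### Patients can be withdrawn after randomization on what the exam shows, and the plan does not clearly keep them in the ADR analysis

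*Combined protocol and SAP*

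**What the plan says.** Study procedures fixes the order of events: "Patients agreeing to participate will be randomized to one of the four study arms prior to initiation of colonoscopy". Under Methods, patients are "randomized to undergo a standard colonoscopy, a Fuse colonoscopy, colonoscopy with EndoCuff or a colonoscopy with EndoRings", so the arms differ by instrument or by tip attachment. No blinding is described.

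Study procedures then lists three grounds for withdrawal after randomization. Two come from the exam: a "condition discovered during colonoscopy which places the patient in the exclusion criteria, an inadequate bowel preparation as determined by the performing doctor". The third is the patient's own request. The phrase about the performing doctor attaches to bowel preparation; who rules on a discovered condition is not stated.

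Statistical analyses defines two sets: "We will perform analyses on the data after randomization and prior to withdrawal (intention to treat) and on data of patients completing the study". The second, called per protocol, leaves out withdrawn patients. Neither set is named primary. The primary test is given as follows: "The primary aim of increased ADR detection will be tested using a chi-square test among the four groups".

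Sample size requires 388 patients per arm and raises this to 412 to allow for an average of 6% withdrawals after randomization.

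**The concern.** Randomization makes the arms comparable at the moment of allocation. A later removal keeps that comparability only if it is unrelated to the arm or unrelated to the outcome. Here the judgement on preparation is made during the exam that yields the outcome, by an operator who will in practice know the device. There is no scale, threshold or independent check, and nothing places the judgement ahead of polyp detection. A poorly cleaned exam with no adenoma is the natural candidate for removal, and removing it raises that arm's ADR.

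The rule also sits badly with the Introduction, which defines ADR over all colonoscopies that a doctor performs. A withdrawn patient whose exam took place is a performed colonoscopy that may drop out of the denominator.

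The primary comparison is at stake: a device could appear to raise detection, or fail to, partly because of who was removed.

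**Working it through.** **1. The plan's own figures.** Inputs from Sample size: ADR 40% against 50%, α 0.05 (taken as two-sided), power 80%, withdrawals 6%.

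n = [1.96·√(2·0.45·0.55) + 0.8416·√(0.40·0.60 + 0.50·0.50)]² / 0.10² = [1.379 + 0.589]² / 0.01 = 387.3, so 388. This matches the plan.

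388 × 1.06 = 411.3, so 412; division by 0.94 gives 413. The difference of one patient is immaterial. Expected withdrawals are 412 × 0.06 ≈ 25 per arm, leaving about 387. The inflation therefore treats withdrawn patients as not counting toward the 388.

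**2. Bias if withdrawals are deleted.** Assumptions, not given in the documents: true ADR 40% in every arm, 6% withdrawn in every arm, standard-arm withdrawals unrelated to outcome, and ADR q among patients withdrawn from a device arm.

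Device ADR among those retained = (0.40 − 0.06·q) / 0.94

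- Pairwise error: with d the bias and SE = √(2·0.40·0.60/388) = 0.0352, the rejection probability is Φ(−1.96 − d/SE) + 1 − Φ(1.96 − d/SE).
- Four-group chi-square, 3 df: noncentrality λ = 388·Σ(pᵢ − p̄)² / [p̄(1 − p̄)].

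| q | Device ADR | Bias (points) | Pairwise error | Four-group error |
|---|---|---|---|---|
| 0% | 0.40/0.94 = 42.6% | +2.6 | about 11% | about 10% |
| 20% | 0.388/0.94 = 41.3% | +1.3 | about 6.5% | about 6% |
| 40% | 0.376/0.94 = 40.0% | 0 | 5% | 5% |

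For q = 0, d/SE = 0.0255/0.0352 = 0.73. With one device arm shifted λ = 0.79, and with all three shifted λ = 0.78; both give about 10%. If withdrawals in every arm are equally selected, numerator and denominator change alike and the bias is about zero.

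**3. Power if everyone who starts is kept.** Power = Φ{[δ√n − 1.96·√(2p̄(1 − p̄))] / √(p₁(1 − p₁) + p₂(1 − p₂))}, with n = 412.

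- No dilution, 40% against 50%: 82%.
- Assumed 6% of exams with half the ADR (20% and 25%): overall 38.8% against 48.5%, power 80%.
- Assumed 6% of exams all without an adenoma: overall 0.94·40% = 37.6% against 0.94·50% = 47.0%, power Φ[(1.908 − 1.369)/0.6955] = 78%.

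**The case against.** The strongest reply is that an intention-to-treat analysis is already planned. Its sentence contrasts randomized patients with completers, and can be read as the full randomized set before anyone is removed. On that reading the bias is confined to per protocol. This stands as a possible reading, so it cannot be said that the plan will lose these patients' data. But the wording can also mean data collected up to the moment of withdrawal, no adenoma status is assigned to a withdrawn patient, neither set is primary, and the 6% inflation points the other way.

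The second reply is that the 42.6% and 11% figures are extreme. That is right. They require deletion of withdrawals and one-sided selection of every withdrawn device-arm patient, although the 6% also covers patients' own requests.

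A reader might infer more than the text supports in three places.

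- **The operator has always seen the colon before deciding.** No timing is stated, and poor preparation may be evident during insertion. The gap is that nothing prevents a later judgement.
- **A failed insertion could be relabelled as an exclusion.** The criterion is "Anticipated difficult colonoscopy", by its wording a judgement made beforehand. Its use for a stalled exam is conjecture.
- **Polyposis found at the exam would inflate a device arm.** The criterion reads "Any personal h/o large bowel resection, inflammatory bowel disease, or polyposis syndromes", a history item. If such a patient were dropped, an adenoma-positive patient would usually be lost, which lowers that arm's ADR.

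**Conclusion.** The concern holds as a gap in the design. The preparation criterion is subjective, is applied without blinding during outcome measurement, and can remove randomized patients from an analysis that is not clearly required to keep them. That the operator knows the arm is an inference from the devices and the absence of any blinding, but it is hard to avoid.

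Under the stated assumptions, and only for an analysis that deletes withdrawals, the spurious gain runs from zero to 2.6 points against a 10-point target. The documents do not give the ADR among withdrawn patients, so the true size is unknown and its direction is not fixed. A reader might conclude that the trial is biased in favour of the devices; the documents support only that it is open to bias. The sample-size calculation itself is sound. This should be corrected, with medium confidence in its practical effect.

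**What to change.** In Statistical analyses, define the primary intention-to-treat set as all randomized patients who start colonoscopy, in the arm to which they were randomized. Take adenoma status (yes or no) from the exam as actually performed, and count an incomplete exam with what was found.

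In Study procedures, state that inadequate preparation or a condition discovered during the exam is recorded, but removes a patient only from the per-protocol analysis. Label that analysis a sensitivity analysis. Report withdrawals by arm and reason, with patients' own requests listed separately.

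The change is to wording only. It concerns who is analysed, not how an exam is conducted or when it is stopped. The downside is some dilution from poorly prepared exams, which need not be exactly equal across arms. The 412 per arm already planned exceeds the required 388, so no extra patients are needed; under the dilution assumptions shown, power is about 78% to 80%.

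### Does the plan need to say which analysis set is primary for the ADR chi-square and how withdrawn patients are counted?

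*Combined protocol and SAP*

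**What the plan says.** The Statistical analyses section names two sets: "We will perform analyses on the data after randomization and prior to withdrawal (intention to treat) and on data of patients completing the study", the second being explained as "excluding the withdrawal patients, per protocol". The next sentence gives the primary test: "The primary aim of increased ADR detection will be tested using a chi-square test among the four groups". It does not link that test to one of the sets.

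Study procedures gives three routes to withdrawal after randomisation. In the first, "a patient can be withdrawn due to condition discovered during colonoscopy which places the patient in the exclusion criteria". The other two are "an inadequate bowel preparation as determined by the performing doctor or a request from the patient to be withdrawn".

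The Sample size section states that "we require 388 patients in each arm at an α level of 0.05 with 80% power", for a 10-point rise from 40%. It then enrols 412 per arm (1648 in all) with this reason: "To account for the withdrawals after randomization, which would amount to an average of 6% per our recent studies".

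The Introduction defines ADR as the share of patients with one or more adenomas, with all colonoscopies done by a doctor as the denominator.

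**The concern.** Two analysis sets and one primary test, with no link between them, leave room to choose the headline result after the data are seen. The sections also seem to pull apart. The intention-to-treat label suggests everyone randomised, while 388 is the number meant to remain after withdrawals, which suggests completers.

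The counting rule looks open too. A condition found during colonoscopy, or a bowel judged too poorly prepared, may come to light after adenomas have been seen. Such a patient could be counted by what was found, counted as having no adenoma, or treated as missing. The phrase about data before withdrawal could mean the data gathered up to that point, or the set of patients before withdrawals are removed.

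At stake would be the false-positive rate of the primary test if the better result were picked. If withdrawal differed between arms, the size of the ADR difference would also be affected.

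**Working it through.** **Inputs.** From Sample size: ADR 40% against 50%, α 0.05 (two-sided reproduces the figure), 80% power, 388 and 412 per arm, 6% withdrawal. Assumed: withdrawal is equal in every arm, and ADR among the withdrawn is r times that of completers, with r = 0, 0.5 or 1. The documents do not give r.

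**1. The plan's own figure.** Pooled two-proportion formula:

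n = [1.960 × √(2 × 0.45 × 0.55) + 0.842 × √(0.40 × 0.60 + 0.50 × 0.50)]² / 0.10² = 387.3, so 388.

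For withdrawals, 388 / 0.94 = 412.8 and 388 × 1.06 = 411.3; the stated 412 fits to within one patient. After 6% loss, 412 × 0.94 = 387.3 remain.

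**2. Does 412 serve both sets?** ADR in all randomised patients, with adenomas counted as found, is 0.94p + 0.06pr. Unadjusted pairwise power:

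| Set | ADRs compared | n per arm | Power |
|---|---|---|---|
| Completers | 40.0% vs 50.0% | 387 | 80.0% |
| All randomised, r = 1 | 40.0% vs 50.0% | 412 | 82.4% |
| All randomised, r = 0.5 | 38.8% vs 48.5% | 412 | 80.3% |
| All randomised, r = 0 | 37.6% vs 47.0% | 412 | 78.1% |

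The last row is also the result of counting every withdrawn patient as having no adenoma. The difference is then 9.4 points instead of 10.0. Either set has close to the planned power.

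**3. How often would the conclusion change?** Trials were simulated with four arms of 412 and binomial 6% withdrawal in each. The four-group chi-square was run on completers and on all randomised patients counted as found, over r = 0, 0.5 and 1.

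| True effect | Opposite sides of 0.05 |
|---|---|
| None | about 2% to 2.5% |
| 10 points (planned) | about 5% |
| 7 points (assumed) | 7% to 9% |

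With no effect, each test alone rejects in 5.0% of trials, and at least one of the two rejects in about 6%. Adding a third version, all withdrawn counted as negative, brings the chance that any one rejects to 6.0% to 7.0%.

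**4. An example near the threshold.** Take 24 withdrawn per arm, with adenomas in 155, 155, 155 and 187 of 388 completers. The mean is 163, so the squared deviations sum to 3 × 8² + 24² = 768.

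- Completers: pooled rate 652/1552 = 0.4201; χ² = 768 / (388 × 0.4201 × 0.5799) = 8.12 on 3 df, p = 0.0435.
- Withdrawn all counted as negative: pooled rate 652/1648 = 0.3956; χ² = 768 / (412 × 0.3956 × 0.6044) = 7.80, p = 0.0504.
- Withdrawn counted as found at about the completers' rates (10, 10, 10 and 12 of 24): 165, 165, 165 and 199 of 412, mean 173.5; χ² = (3 × 8.5² + 25.5²) / (412 × 0.4211 × 0.5789) = 867 / 100.4 = 8.63, p = 0.035.

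These counts were chosen to straddle 0.05. The crossing comes from a rule that the documents never propose and that discards adenomas already seen.

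**5. The sections side by side.** Enrolling extra patients against expected loss is routine and names no primary set. Statistical analyses commits to both analyses, and step 2 shows that 412 supports both, so the sections do not conflict. The intention-to-treat label together with the Introduction's definition suggests that a patient who had a colonoscopy counts by whether an adenoma was found, and that one with no colonoscopy is outside the denominator.

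**The case for a change.** The strongest case for a change is that this is the primary endpoint and that naming a set costs one sentence. Listing intention to treat first does not designate it as primary. One withdrawal reason rests on the performing doctor's judgement and another arises during the procedure, both after randomisation, so withdrawal could differ by arm. As an illustration, suppose withdrawn patients count as negative and withdrawal is 4% in control and 8% on a device. The ADRs are then 0.96 × 40% = 38.4% and 0.92 × 50% = 46.0%, a gap of 7.6 points. With the withdrawal rates swapped, the gap is 48.0% − 36.8% = 11.2 points.

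Part of this stands. No sentence ranks the two sets, and the Introduction's definition is a general one, not an analysis rule. The status of an examination stopped early, and of a patient who withdraws permission to use data, is not written down. But the unequal rates are assumptions with no support in the documents, and the shifts also depend on counting the withdrawn as negative. Inflation of the false-positive rate requires selecting the better result, whereas the plan says that both analyses will be performed. What remains is a preference for more explicit wording.

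**Conclusion.** The plan does not name a primary analysis set for the ADR chi-square, and it leaves partial or absent examinations to the analyst. This is a gap in detail and not an error: no stated rule or figure is wrong, and the sample size does not contradict the analysis section. An analyst would take intention to treat as the main result and per protocol as the check, which is the conventional choice, and would count adenomas as found.

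With equal 6% withdrawal, the choice moves unadjusted pairwise power by about 2 points either way around 80%. It changes the four-group conclusion in about 2% to 2.5% of trials with no effect and about 5% at the planned effect. The cost in false positives is about one percentage point, and only if the better of the two results is selected.

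These figures rest on equal withdrawal across arms and on an ADR among the withdrawn between zero and the completers' rate. The documents neither show nor exclude unequal withdrawal. No change to the plan follows.

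### The only primary test is a four-group chi-square, which cannot show that any device raises ADR over standard, although that is the aim and the basis of the sample size

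*Combined protocol and SAP*

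**What the plan says.** The Introduction sets a directional aim with standard colonoscopy as the reference: "We therefore propose to identify the increase in ADR with 3 of these devices compared to standard colonoscopy". The title agrees, describing the trial as one for improving ADR. The Sample size section repeats the comparison ("We hope to achieve a 10% increase in the ADR with these newer devices when compared to standard colonoscopy") and sizes the trial on it: "to detect a 10% increase from a baseline of 40%, we require 388 patients in each arm", at α 0.05 and 80% power.

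The Statistical analyses section gives one test for this aim: "The primary aim of increased ADR detection will be tested using a chi-square test among the four groups". The document contains no device-versus-standard contrast, ADR difference, confidence interval, sidedness, follow-up procedure or rule for multiple comparisons.

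**The concern.** A chi-square test on a table of four arms by adenoma yes/no asks whether the four ADRs are all equal. It does not use the arm labels. A small p-value says that some arm differs from some other. It does not say that ADR went up, or with which device.

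If the plan is followed exactly, a significant primary result does not by itself support a claim that any device raises ADR. That claim would rest on comparisons whose test and error rule are nowhere written. Both can be fixed credibly only before outcome data are seen.

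**Working it through.** **Inputs.** Standard ADR 40%, target 50%, α 0.05, power 80%, 388 per arm (Sample size); four arms (Methods); equal allocation, implied by the equal arm sizes. Sidedness is not stated; two-sided is assumed because it reproduces the plan's figure.

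**1. Which comparison does 388 belong to?** Pooled-variance formula for two proportions, 1:1:

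n = [z₀.₉₇₅·√(2·p̄·q̄) + z₀.₈₀·√(p₁q₁ + p₂q₂)]² / (p₂ − p₁)²

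With p̄ = 0.45: n = [1.960·√0.495 + 0.842·√0.490]² / 0.10² = 387.3, so **388 per arm**. This matches the plan exactly. The alternatives do not:

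- One-sided: 305. Continuity-corrected: 408. Relative 10% increase (40% to 44%): 2389.
- Three devices pooled against standard (3:1), same formula: [1.960·√0.3325 + 0.842·√0.3233]² / 0.10² = 258.8, so 259 in the standard arm.
- Four-group chi-square: 356, 270 or 363 per arm with one, two or three devices at 50% (step 2).

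The sample size is therefore that of one device against standard.

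**2. Power of the stated test.** Noncentrality λ = n·Σ(pᵢ − p̄)² / [p̄(1 − p̄)], 3 df, critical value 7.815. With one effective device, p̄ = 0.425 and λ = 388 × 0.0075 / 0.2444 = 11.91.

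| Devices at 50% | One | Two | Three |
|---|---|---|---|
| λ at 388 per arm | 11.91 | 15.68 | 11.67 |
| Power at 388 per arm | 83.7% | 92.9% | 82.9% |
| n per arm for 80% power | 356 | 270 | 363 |

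Power is not the problem.

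**3. Direction.** Take 194/388 in one arm and 155/388 in each of the other three. Then chi-square = 12.03, p = 0.007, whether the high arm is a device or standard. With one device at 30% and the other three arms at 40%, so that no device helps, the test still has 85.4% power to reject.

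**4. What a rejection leaves open.** Simulation with four binomial arms, 388 each, 400,000 trials per scenario. A device counts as significantly better if its pairwise pooled z against standard exceeds 1.96.

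| Devices at 50% | One | Two | Three |
|---|---|---|---|
| Chi-square rejects | 83.6% | 93.0% | 83.2% |
| Of rejections: no device significantly better | 11.0% | 5.2% | 0.02% |
| Of rejections: at least one effective device not significantly better | 11.0% | 27.3% | 28.2% |
| Power for a given effective device, unadjusted pairwise test after a significant chi-square | 74.4% | 77.9% | 74.1% |

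With one effective device, 0.836 × 0.110 gives about 9% of all trials that reject while no device is significantly better.

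**5. Error under possible follow-ups.** The plan names none, so both are assumptions.

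- *Unadjusted pairwise tests only after a significant chi-square.* Under the global null, about 4.0% of trials flag any device. With one effective device, at least one of the two ineffective ones is flagged as different from standard in 9.1% of trials (as better in 4.6%).
- *Three unadjusted tests with no gate.* Under the global null, 12.9% flag at least one device.

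**The case against.** The strongest reply is that the gap is narrower than it looks. The test is valid at 5% and well powered, and it would be read beside the four observed ADRs. Under the plan's own 40% versus 50%, when the test rejects, the arm with the highest ADR is a truly effective device in more than 99% of trials. The aim already fixes the reference arm, so three contrasts follow naturally. The 12.9% belongs to a procedure the plan does not describe; behind the four-group gate the global-null rate is about 4.0%, and false claims of improvement with one effective device stay at 4.6%. The 27–28% is largely a limit of 388 per arm, which naming the contrasts does not remove: when all three devices work, all three unadjusted pairwise tests are significant in only 60.4% of trials.

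Much of this stands. The direction gap almost vanishes if every device works, and the error inflation depends on a follow-up the plan never chose. The per-device reading is also an inference, since the text speaks of the newer devices collectively. But reading direction and device off the observed rates is an informal step with no stated error rate. A reference arm implied by the aim is not a specified test, interval or error rule. Nor does the collective reading rescue the plan, because the four-group test does not test pooled devices against standard either.

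**Conclusion.** The concern holds. Aim and sample size are device-versus-standard; the sole primary test is a non-directional test of equality over four arms. The fault is not validity or power but that the result does not answer the question asked, and the comparisons that would answer it are unspecified. Its size depends on how many devices work: the share of significant results with no device significantly better than standard is about 11%, 5% and 0.02% with one, two and three effective devices, while failure to identify every effective device is 27–28% with two or three.

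These figures assume 388 evaluable patients per arm, true ADRs of 40% or 50%, and two-sided pairwise tests at 0.05. The conclusion that the test shows neither direction nor device needs none of these assumptions. This should be corrected before outcome data are examined.

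**What to change.** In Statistical analyses:

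- Make the primary analysis three prespecified comparisons, each device against standard, each reported as an ADR risk difference with a confidence interval. Say whether the intervals are unadjusted or simultaneous.
- State how error over the three is handled: closed procedure, Dunnett, Holm, a fixed sequence with its order given, or no adjustment with a stated rationale.
- Keep the four-group chi-square, if wanted, as supportive or as step one of a closed procedure. In the latter, a device is declared different from standard only if the four-group test, both three-group tests containing that device and standard, and the pairwise test are all significant at 0.05. Direction comes from the sign of the difference.
- Label device-versus-device comparisons exploratory.
- If a pooled devices-versus-standard claim is meant instead, say so and name that contrast. Its power at 388 versus 1164 is 93.0%.

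In Sample size, state sidedness and restate power for the chosen rule. At 388 per arm, per-device power is:

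| Rule | Power |
|---|---|
| Unadjusted | about 80% |
| Closed procedure | 71–72% |
| Holm | 65–73%, depending on how many devices work |
| Dunnett | 67.5% |
| Fixed sequence | about 80% for the first device; about 60% for the third even if all work |

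The cost is text in two sections, with no new data. The downside is that closed testing, Holm and Dunnett all fall short of 80% if the stated power is meant per device. The sponsor must then accept the lower figure or enrol more: Dunnett at 80% per device needs about 503 evaluable patients per arm (4 × 503 = 2012, against 1552).
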